Study design (cont'd):	
Once a SRA737-related, Grade 2 toxicity is observed in a dose escalation cohort during Cycle 1, that cohort will be expanded to 3 to 6 subjects, and subsequent dose level cohorts will follow a rolling 6 design (see Section 3.3 for additional details). Dose escalation with an alternative schedule may begin at any time and may either run either in parallel or instead of continued escalations in the continuous schedule. The final number of subjects enrolled into the trial is dependent on the number of dose levels explored in the Dose Escalation Phase. Patients who are not evaluable for assessment of dose limiting toxicity (DLT) may be replaced.
 
Stage 2: A Cohort Expansion Phase
 
The Cohort Expansion Phase consists of 6 indication-specific expansion cohorts of approximately 20 prospectively-selected genetically-defined subjects each (namely, subjects with previously treated metastatic colorectal cancer [CRC], high grade serous ovarian cancer [HGSOC] without CCNE1 gene amplification, HGSOC with CCNE1 gene amplification (or alternative genetic alteration with similar functional effect), metastatic castration-resistant prostate cancer [mCRPC], advanced non-small cell lung cancer [NSCLC], and squamous cell carcinoma of the head and neck [HNSCC] or squamous cell carcinoma of the anus [SCCA]). This allows for a preliminary exploration of the efficacy of SRA737.
 
The goal of the expansion cohorts is to assess SRA737 across multiple tumor types in subjects who have a range of genomic profiles of interest as described in inclusion criterion 9. The Sponsor may choose to refine or select particular genomic profile requirements in each (or all) Expansion Cohort(s) based on observations of tumor response and clinical benefit in the ongoing study and/or other emerging clinical and nonclinical data. The Sponsor may also choose to select for alternative genomic profiles in the event profile(s) not associated with tumor responses are over-represented in subjects already enrolled.
 
Intensive PK and ECG monitoring for QTc assessments will be collected until the Sponsor determines sufficient data have been collected and analyzed across the study as a whole. Tissue (archival or fresh) and blood will be collected for prospective genetic analysis to determine eligibility. See Section 7.1.1 for more details.
 
Prospective screening of subjects within the selected indications to determine eligibility based on tumor genetics will begin prior to the completion of dose escalation. Eligibility will be determined by the Sponsor's review of genetic abnormalities detected in genes in the categories listed in inclusion criterion 9. Enrollment to Dose Escalation and Expansion Cohorts may occur in parallel.
 
A subject that qualifies for the Cohort Expansion Phase will be enrolled into a Dose Escalation Cohort whenever possible. Any such subject will be considered to have enrolled in both phases simultaneously. Only when a dose escalation enrollment slot is not available for an eligible genetically-defined subject, that subject may be enrolled to an expansion cohort and treated with SRA737 at the highest dose level previously determined to be safe. Intra-subject dose escalation is allowed for these, and for all, study subjects.

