3 TRIAL DESIGN

3.1 CLINICAL TRIAL OBJECTIVES AND ENDPOINTS

3.1.1 PRIMARY OBJECTIVES AND ENDPOINTS

Primary objectives	Endpoints
To establish the safety profile of SRA737	Safety parameters (referencing National Cancer Institute – Common Terminology Criteria for Adverse Events [NCI-CTCAE] v4.03) including: incidence, seriousness, severity and causality of each AE to SRA737, timing of AE onset, AE duration, and AEs leading to interruption, modification, or discontinuation of study treatment, and primary reason for discontinuation of study treatment if other than disease progression (PD), laboratory (eg, clinical chemistry, hematology, urinalysis) and vital sign data
To determine the MTD with 1 or more schedules of administration of SRA737	The highest dose at which $\leq 33\%$ of subjects have a dose limiting toxicity (DLT) in a cohort of up to 6 subjects
To propose a recommended Phase 2 dose and schedule of SRA737	A safe and well tolerated dose and schedule that provides high exposure, based on all available PK, PDn, and safety parameter data from all cycles of therapy
To evaluate the preliminary efficacy of SRA737 including efficacy in prospectively-selected genetically-defined subjects enrolled into indication-specific expansion cohorts	Objective response rate (ORR) Disease control rate (DCR) Time to response (TTR) Duration of response (DOR) Progression-free survival (PFS) Time to progression (TTP) Overall survival (OS)

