Intensive PK and ECG monitoring for QTc assessments will be performed for subjects in the Cohort Expansion Phase. However, the Sponsor may reduce or modify the requirements for PK sampling, including elimination or modification of the Day -7 to Day -4 visit, once sufficient data to evaluate the PK of SRA737 have been collected and analyzed. If this occurs, the modified requirements will be documented by an update to the appropriate study documents.

Tissue (archival or fresh) and blood will be collected for prospective genetic analyses to determine eligibility. See Section 7 for more details.

Prospective determination of tumor genetics to determine eligibility of subjects within the selected indications may begin prior to the completion of dose escalation.

Enrollment to the Dose Escalation and Expansion Cohorts may occur in parallel. A subject that qualifies for the Cohort Expansion Phase will be enrolled into an Escalation Cohort whenever possible. Any such subject will be considered to have enrolled in both phases simultaneously. Only when a dose escalation enrollment slot is not available for an eligible prospectively-selected genetically-defined subject, that subject may be enrolled to an expansion cohort and treated with SRA737 at the highest dose level previously determined to be safe. Intra-subject dose escalation is allowed for these, and for all, study subjects when a higher dose level has been determined to be safe in a cohort of Dose Escalation subjects.

[figure not shown]
Enrollment into the Expansion Cohorts requires that each subject's tumor has evidence of a combination of mutations which are expected to confer sensitivity to

Chk1 inhibition. Eligibility will be determined by the Sponsor's review of genetic abnormalities listed in Appendix 6.

Figure 6 Study Design

Dose escalation increments will be determined by cohort review process.

The dose of SRA737 will be doubled in subsequent cohorts until a subject in any cohort experiences a SRA737-related or probably related NCI CTCAE \geq Grade 2 toxicity; cohorts will then be expanded to 3-6 subjects following a rolling 6 design for that and subsequent cohorts, and, in the absence of a DLT, the dose of SRA737 will be escalated in less than 100% increments (typically 25-75% increments).

DLT = dose-limiting toxicity, NCI CTCAE = National Cancer Institute Common Terminology Criteria for Adverse Events, TBD = to be determined, MTD = maximum tolerated dose

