3.7 INTRA-SUBJECT DOSE ESCALATIONS

Once a higher dose level has been determined to be safe in a cohort of Dose Escalation subjects, subjects who have not experienced \geq Grade 2 SRA737-related toxicity at the dose at which they are currently being treated, in the most recent prior cycle, are able to escalate to the next higher dose level for that schedule once the sponsor approves the escalation.

Only one dose level increase can be undertaken each cycle.

This intra-subject escalation will be to a dose level already evaluated at a Cohort Review Meeting and found to be acceptable from a safety perspective. If the subject(s) then goes on to experience an event meeting the definition of DLT, this information will be taken into account for future dose escalation decisions.

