**Table 1: Data Display for Study Population and Efficacy**

Column Text Display	Description Verbatim terms included in the grouping (including misspelling and specific terms present in the clinical data)	Display Order
CRC	Metastatic Colorectal Cancer Metastatic colorectal Metastatic Colorectal Carcinoma With Abdomial* Mass Colorectal Adenocarcinoma	1
HGSOC	High Grade Serous Ovarian Cancer Platinum resistant ovarian Carcinosarcoma Of Ovary – CCNE1 Amplification: No High grade serous ovarian cancer Platinum-Resistant High Grade Papillary Serous Carcinoma Of The Ovary Serous Adenocarcinoma Peritoneum/Ovary	2
NSCLC	Advanced Non-small cell Lung Cancer Advanced non small cell lung	3
mCRPC	Metastatic Castration-Resistant Prostate Cancer Metastatic castration resistant* prostate Prostate Adenocarcinoma Adenocarcinoma of Prostate	4
HNSCC/SCCA	Head and Neck Squamous Cell Carcinoma Head and neck squamous cell	5
	Squamous cell carcinoma of the anus	
Other	Disease types not included in the previous columns	6
Overall	All subjects in the population	7

\* Misspelling are present in the clinical database and will be kept verbatim for programming purposes

For safety summaries, the columns will be group based on Cycle 1 Day 1 total dose level. For subjects without Day 1 treatment they will be included in the “<=800mg” column.

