**Table 2: Data Display for Safety**

Column Text Display	Description	Display Order
<=800mg	SRA737 daily total dose <= 800 mg	1
>800mg	SRA737 daily total dose > 800 mg, including BID dosing frequency	2
Overall	All subjects in the population	3

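### Safety tables fix each subject's dose column at Cycle 1 Day 1, so an event that begins above 800 mg in a subject who started at or below 800 mg is shown under ≤800 mg, and no planned table shows dose at onset

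*SAP*

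**What the plan says.** SAP Section 9.2.1, in the text between Tables 1 and 2, sets the rule: "For safety summaries, the columns will be group based on Cycle 1 Day 1 total dose level". Table 2 then gives three columns: ≤800 mg, >800 mg ("SRA737 daily total dose > 800 mg, including BID dosing frequency") and Overall. A subject who took only the PK run-in dose goes into the ≤800 mg column by default ("For subjects without Day 1 treatment they will be included in the" ≤800 mg column), whatever that dose was.

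SAP Section 12.2 counts an AE as treatment-emergent if it starts or worsens at any time after the first dose, so later cycles are included.

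The protocol lets dose change within a subject. Section 3.2: "Intra-subject dose escalation is allowed for these, and for all, study subjects when a higher dose level has been determined to be safe". Section 3.7 adds conditions. The subject must have had no Grade 2 or higher "SRA737-related toxicity at the dose at which they are currently being treated, in the most recent prior cycle". The higher level must already have been accepted at a Cohort Review Meeting, and the sponsor must approve. The pace is limited: "Only one dose level increase can be undertaken each cycle".

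Protocol Section 11.2.2 plans TEAE reporting at each dose level. Protocol Section 3.1.1 says the RP2D is to be "based on all available PK, PDn, and safety parameter data from all cycles of therapy".

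**The concern.** Dose is a time-varying exposure in this trial, but the safety tables treat it as a baseline attribute. Those who move up are, by the escalation rule, subjects who tolerated the lower dose. If one of them starts at or below 800 mg, passes 800 mg and then has a first event, the table credits it to the dose that was tolerated. The time spent above 800 mg appears in no dose-specific denominator.

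The safety profile and the RP2D are primary objectives, and someone using these tables to compare doses could not detect or undo the misplacement. The list of tables in SAP Section 16.1 includes none by dose at onset, highest dose or individual dose level. SAP Section 12.1 specifies only treatment duration and Cycle 1 compliance, although Protocol Section 11.2.1 promises a description of dose modifications.

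**Working it through.** The plan states no figure on this point, so there is none to reproduce. The check has three parts.

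**1. When is the column wrong?** Set the SAP grouping rule beside the protocol's dosing rules:

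| Starting dose | Dose at AE onset | Column shown | Matches onset dose? |
|---|---|---|---|
| ≤800 mg | ≤800 mg, including after escalation within the band | ≤800 mg | Yes |
| ≤800 mg | >800 mg after escalation | ≤800 mg | No |
| >800 mg | >800 mg | >800 mg | Yes |
| >800 mg | ≤800 mg after reduction | >800 mg | No |

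Only crossings of 800 mg are misfiled. The PK-only default adds a possible mismatch if the single dose exceeded 800 mg.

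**2. Can a subject cross?** Protocol Section 2.6 documents a 600 mg cohort (n=1). Protocol Section 3.3 gives typical steps of 25–75% once accelerated titration ends. The step needed from 600 mg to reach 800 mg is 800/600 − 1 = 33.3%, and a larger step crosses the cut.

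- 25% step: 600 × 1.25 = 750 mg, still in the ≤800 mg band
- 50% step: 600 × 1.50 = 900 mg, crosses
- 75% step: 600 × 1.75 = 1050 mg, crosses

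One escalation from 600 mg could therefore cross at Cycle 2, if such a level had been cleared. From 300 mg (the threshold used in SAP Section 8.2), crossing would need more than 800/300 − 1 = 166.7%. A single step below 100% cannot do that, so several cycles would be needed.

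**3. What could it do to the table?** The documents give neither event rates nor the share of subjects who crossed, so the inputs below are assumptions. Let pL be the risk of the event at ≤800 mg, pH the risk above 800 mg, and f the share of low starters who later cross. If crossing is independent of earlier events, the displayed incidence is

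low column = pL + f × (1 − pL) × pH.

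For pL = 20%, pH = 40% and f = 25%: 0.20 + 0.25 × 0.80 × 0.40 = 0.28. The displayed contrast is 40 − 28 = 12 points, against 20 by dose at onset.

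| pL / pH | f = 10% | f = 25% | f = 50% |
|---|---|---|---|
| 10% / 30% | 12.7% (contrast 17.3) | 16.8% (13.2) | 23.5% (6.5) |
| 20% / 40% | 23.2% (16.8) | 28.0% (12.0) | 36.0% (4.0) |
| 30% / 50% | 33.5% (16.5) | 38.7% (11.3) | 47.5% (2.5) |

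The formula ignores dose reductions, differences in time at risk, and any lower risk among subjects selected for tolerance. It shows a mechanism and a range, not an estimate for this trial.

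**The case against.** Starting-dose grouping is a defensible convention. Each subject appears once, the denominator is clean, and Protocol Section 11.2.3 itself uses the enrolled dose level for response subgroups. The analyses are descriptive. Protocol Section 11.2.2 speaks of dose levels and does not mention dose at onset. These points stand. They are reasons to keep the planned tables, but they do not supply the missing information.

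Exposure to the problem may also be limited. Expansion subjects without an escalation slot start at the highest level already found safe, so they can move up only after a further level is cleared. The documents do not name the levels cleared above 600 mg. This also stands, and it is why no size can be given.

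A reader might infer more than the text supports:

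- **That every AE is misattributed, or that any subject may step up each cycle.** Escalation is conditional, only crossings of 800 mg change the column, and neither the Overall column nor Table 14.3.2.1.2 (AEs by disease category) depends on starting dose.
- **That the dose–toxicity gradient is flattened.** That is plausible but not established. The >800 mg column still describes subjects who start there. Adding tolerant escalators could lower its rate, and dose reductions misfile events in the opposite direction.
- **That the MTD is compromised.** The DLT window in Protocol Section 3.4 closes at the end of Cycle 1, and Section 3.7 says DLT-type events after within-subject escalation inform later decisions. A DLT listing is also planned.

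The RP2D draws on more than these tables, and AE and exposure listings are planned. However, the SAP does not say that the AE listing shows dose at onset, and listings give no incidences.

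**Conclusion.** The point holds in a limited form. Under SAP Section 9.2.1, a TEAE that begins above 800 mg in a subject who started at or below 800 mg is counted under ≤800 mg, and that subject's exposure above 800 mg is absent from the >800 mg column. After a reduction from above 800 mg, later events stay in >800 mg. The crossing is feasible from the documented 600 mg level with any step above 33.3%.

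The effect may inflate the ≤800 mg incidence and narrow the contrast between columns. The actual size is unknown: it depends on how many subjects crossed, which the documents do not report, and the illustrative figures rest on assumed risks and crossing shares.

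Separately, SAP Section 13 does not list the move from reporting at each dose level (Protocol Section 11.2.2) to two starting-dose bands. This is a worthwhile improvement to the reporting of a primary objective. It does not invalidate the planned safety analysis.

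**What to change.** Keep the starting-dose tables and make four additions.

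1. In SAP Sections 9.2.1 and 12.2, add supplementary versions of the overall AE summary and of the Grade ≥3, serious and treatment-related TEAE tables, grouped by daily dose at AE onset. Define this as the last dose taken on or before onset. Give two denominators per dose band: subjects ever treated in it, and person-time in it.
2. Flag events whose onset date was imputed under SAP Section 9.2.3, and show a sensitivity count without them. This is needed because a partial start date in the same month (or, if the month is missing, the same year) as first treatment is set to the first treatment date, which would return the event to the starting dose.
3. Add highest dose received and number of subjects escalated to Table 14.3.1.
4. List the departure from Protocol Section 11.2.2 in SAP Section 13.

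The cost is a few extra tables. SAP Section 11.4 indicates that treatment start and end dates are on the dosing forms. The case report form itself is not in the documents, so it should be checked that each dose change is dated.

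The added tables have limits that should be footnoted. A subject can appear in more than one column, a delayed effect of an earlier dose is credited to the dose at onset, and escalators are selected for tolerance. The tables are descriptive and supplementary, and no dosing rule changes.

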3.4 DEFINITION OF DOSE LIMITING TOXICITY

The DLT window is defined from the first Day -7 to Day -4 dose until the end of Cycle 1 (up to 35 days).

A DLT is defined as any highly probably or probably SRA737-related event of:

- Grade 4 neutropenia or thrombocytopenia that lasts for > 7 days despite withholding dosing and/or providing supportive care (eg, hematopoietic growth factors)

Note: In the event of a Grade 4 neutropenia or Grade 4 thrombocytopenia, a full blood count must be performed at least on Day 7 after the onset of the event to determine if a DLT has occurred. The investigator must continue to monitor the subject closely until resolution to ≤ Grade 3.

- Febrile Neutropenia
- A ≥ Grade 3 thrombocytopenia with ≥ Grade 3 bleeding
- A ≥ Grade 3 nonhematological toxicity with the following possible exceptions per Cohort Review discussion:
 - Alopecia of any grade
 - Grade 3 or 4 nausea or vomiting in subjects that have not received optimal treatment with anti-emetics
 - Grade 3 or 4 diarrhea in subjects that have not received optimal treatment with anti-diarrheal medication
 - Transient, asymptomatic Grade 3 biochemical abnormalities if agreed by the Medical Monitor and the Chief Investigator
 - Grade 3 fatigue, unless there is an increase by at least 2 grades from baseline (classed as the grade prior to first dose)
- Inability to receive 75% of planned dose in the first cycle during the DLT window due to drug-related toxicity

DLTs defined above will be considered for the purposes of dose escalation decisions; however, should cumulative toxicity become apparent this will also be taken into consideration when determining either the next dose level or the RP2D(s).

All DLTs must be reported to the sponsor or sponsor's delegate within 24 hours of site staff becoming aware of the DLT, including any change made to the grade or causality of an AE that may alter its DLT status, as this may affect dose escalation decision making.

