11.2.2 SAFETY

Safety data will be collected from the date of written informed consent. Safety variables will be summarized by descriptive statistics. Laboratory variables will be described using the NCI-CTCAE v4.03. The MTD for each schedule tested, if reached, and the RP2D and schedule will be described.

Treatment-emergent AEs will be reported for each dose level and coded using a current version of the MedDRA thesaurus, presented as tables of incidence of AEs by body system and by worst severity grade observed. Additional tables will be prepared to summarize incidence of AEs reported as related and unrelated events.

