### 4.1. Primary Endpoints

- Safety parameters including adverse events (AEs), laboratory tests, and vital signs
- MTD: the highest dose at which  $\leq 33\%$  of subjects have a dose limiting toxicity (DLT) in a cohort of up to 6 subjects
- Recommended Phase 2 Dose (RP2D)
- Objective response rate (ORR)
- Disease control rate (DCR)
- Time to response (TTR)
- Duration of response (DOR)
- Progression-free survival (PFS)
- Time to progression (TPP)

- Overall survival (OS)

If there are no subjects with response (complete or partial response), TTR and DOR related summaries and listings will not be generated.

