## 8. ANALYSIS POPULATIONS

### 8.1. Safety Evaluable Population

Safety evaluable population includes all enrolled subjects who receive at least 1 dose of SRA737. Subjects who received the single dose for PK evaluation but never received study treatment during the treatment phase are also included in this population.

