### 12.2. Adverse Events

Adverse events will be coded using MedDRA version 19.1.

An AE will be considered a treatment emergent adverse event (TEAE) if it begins or worsens in severity after the first dose of study treatment (including the dose for PK purpose). Partial AE

start dates will be imputed as detailed in [Section 9.2.3](#). If an AE start date is completely missing it will be considered a TEAE.

Summary tables will be based on TEAEs. The incidence of TEAEs will be presented using counts and percentages of subjects with TEAEs and tabulated by SOC and PT. SOC will be sorted in descending frequency and PT within SOC will be sorted by descending frequency based on the incidence of all subjects in the population. If a subject has multiple occurrences (start and stop) of an event associated with a specific SOC or PT within a SOC, a subject will only be counted once in the incidence count for the SOC or PT within SOC respectively.

An overall summary table of AEs will be presented detailing the number and percentage of subjects for the following categories. One additional overall summary of AEs by disease categories instead of Cycle 1 total dose with the same AE categories below will also be presented.

- At least one TEAE;
- At least one Treatment-Related TEAE;
- At least one Grade  $\geq 3$  TEAE
- At least one Grade  $\geq 3$  Treatment-Related TEAE;
- At least one Serious TEAE;
- At least one Serious Treatment-Related TEAE;
- At least one Serious AE Occurred Prior to First Dose
- At least one TEAE leading to Treatment Withdrawn;
- At least one Treatment-Related TEAE leading to Treatment Withdrawn;

Except for all TEAEs which will be summarized by SOC and PT, the incidence of all other TEAEs by PT will be presented for the following in descending frequency based on the incidence of all subjects in the population.

- All TEAEs;
- Treatment-related TEAEs;
- TEAEs with Grade  $\geq 3$ ;
- Treatment-related TEAEs with Grade  $\geq 3$ ;
- Serious TEAEs;

- Treatment-related serious TEAEs;
- Serious AEs Occurred Prior to First Dose
- TEAEs leading to Treatment Withdrawn
- Treatment-related TEAEs leading to Treatment Withdrawn

A Treatment related AE is defined as an AE for which the investigator classifies the relationship to study treatment as being “Highly probable”, “Probable”, or “Possible” on Adverse Event eCRF. Missing relationship and toxicity grade will be imputed per [Section 9.2.3](#).

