## 13. CHANGES FROM ANALYSES PLANNED IN THE PROTOCOL

The following are the changes from the analyses planned in the protocol

- Protocol section 3.6 defined 6 indication-specific cohorts in the expansion phase. The summaries based on the disease types will be adjusted based on the actual enrollment. Refer to [Section 9.2.1](#) for the definition of each disease type.
- Exploratory objectives and endpoints related to biomarkers in protocol Section 3.1.3 and SAP [Section 4.3](#) were not collected in the study.
- In protocol Section 3.1.3 and SAP [Section 4.3](#) one of the exploratory endpoints is “Association of QT, QTc, blood pressure, heart rate, other ECG intervals with time-matched PK concentrations. Profile of QTc over the dosing interval”. A summary PK report and QTc report will be provided in the clinical study report, but separate analysis of the endpoints listed here will not be done.
- In protocol Section 11 and SAP [Section 6.1](#) timing of interim analyses are specified. These interim analyses will not be presented and justification will be provided in the clinical study report.
- Alternative definition of response evaluable population was added in [Section 8.2](#).

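### Safety tables collapse all dose levels into ≤800 mg and >800 mg, an undeclared departure from the protocol; run-in-only subjects default to ≤800 mg and no table gives DLT n/N by dose

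*SAP*

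**What the plan says.** **Reporting unit.** Protocol 11.2.2 says: "Treatment-emergent AEs will be reported for each dose level". SAP 9.2.1 sets the columns of the safety summaries by total dose on Cycle 1 Day 1. SAP Table 2 then lists three: ≤800 mg, >800 mg and Overall. The second is described as "SRA737 daily total dose > 800 mg, including BID dosing frequency". One further AE overview (Table 14.3.2.1.2) is by disease category.

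**Declared changes.** SAP Section 13 opens "The following are the changes from the analyses planned in the protocol" and lists five: disease-type summaries, biomarker endpoints, the PK/QTc endpoint, the interim reviews and the alternative response-evaluable population. Its one pointer to Section 9.2.1 concerns disease types, not dose columns.

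**Subjects with no Day 1 dose.** SAP 9.2.1: "For subjects without Day 1 treatment they will be included in the “<=800mg” column". On the safety population, SAP 8.1 says: "Subjects who received the single dose for PK evaluation but never received study treatment during the treatment phase are also included in this population". SAP 12.2 counts an AE as treatment-emergent "if it begins or worsens in severity after the first dose of study treatment (including the dose for PK purpose"). Protocol 3.4 says: "The DLT window is defined from the first Day -7 to Day -4 dose until the end of Cycle 1".

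**MTD.** SAP 4.1 keeps the MTD as a primary endpoint: the highest dose at which no more than 33% "of subjects have a dose limiting toxicity (DLT) in a cohort of up to 6 subjects". The only DLT output is Listing 16.2.3.2.5. SAP Table 6 has no DLT table, and SAP Section 8 defines no DLT-evaluable set, although Protocol 3.8.1 does.

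**The concern.** The safety profile and the MTD are primary objectives of this first-in-human trial, and both are questions about dose. Three features of the SAP work against answering them from the planned tables.

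1. AE incidence is shown only on either side of a single cut, so any dose relation below or above 800 mg is invisible. Schedules are not separated, and BID dosing is pooled into the upper column. A reader of Section 13 would not learn that the protocol had promised more.
2. Subjects who took only the run-in dose all go to the lower column. Their events count as treatment-emergent from that dose, so the column label is false for any of them who received more than 800 mg. Early toxicity is one plausible reason for never reaching Day 1, so these subjects may not be typical.
3. The proportion that defines the MTD appears in no table. A listing of DLT events supplies numerators but no denominators, and the default listing order is disease category, site and subject rather than dose.

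**Working it through.** No sample size, power or alpha figure underlies this point, so there is no figure in the plan to reproduce. The check is a comparison of texts plus two pieces of arithmetic.

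**Step 1: text comparison.**

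| Item | Protocol | SAP |
|---|---|---|
| TEAE tables | by each dose level (11.2.2) | ≤800 mg, >800 mg, Overall (9.2.1, Table 2) |
| Departure declared | – | not among the five changes in Section 13 |
| Run-in-only subjects | DLT window opens at the run-in dose (3.4) | in the safety population (8.1), TEAEs counted (12.2), placed in ≤800 mg (9.2.1) |
| MTD | DLT proportion at a dose (3.1.1) | same definition (4.1), no DLT table (Table 6) |

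SAP Section 4 places only secondary and exploratory endpoints outside its scope, so the MTD is inside it. SAP 9.2.2 lets minor format changes pass without a SAP update, but dropping the promised dose levels is not a format change.

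**Step 2: how many levels share the lower column.** Inputs: start at 20 mg/day and steps of at most 100% (Protocol 3.3); a 600 mg cohort with n=1 (Protocol 2.6).

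- Pure doubling gives 20, 40, 80, 160, 320 and 640 mg, then 1280 mg. Six levels are at or below 800 mg.
- Independently of the exact path, reaching 600 mg needs log2(600/20) = log2(30) = 4.91, hence at least 5 steps and at least 6 levels from 20 to 600 mg.
- The column spans 800/20 = 40-fold.

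The actual list of levels is not in the documents.

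**Step 3: effect of the default rule, on assumed counts.** Suppose 22 subjects were treated above 800 mg, 2 of them run-in-only, with severe toxicity in 8/22 against 3/40 in the lower group. The true gap is 36.4% − 7.5% = 28.9 points. Moving the 2 subjects to the lower column gives:

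| Moved subjects with severe toxicity | >800 mg | ≤800 mg | Displayed gap |
|---|---|---|---|
| both | 6/20 = 30.0% | 5/42 = 11.9% | 18.1 points |
| one | 7/20 = 35.0% | 4/42 = 9.5% | 25.5 points |
| neither | 8/20 = 40.0% | 3/42 = 7.1% | 32.9 points |

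The distortion can go either way. It is zero if every run-in-only subject took 800 mg or less.

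**Step 4: why pooled columns cannot stand in for a DLT table, on assumed counts.** Two DLTs among 6 subjects at one level is 33.3% (Wilson 95% interval 9.7% to 70.0%). Pooled with 6, 12, 24 or 44 DLT-free subjects, it becomes 2/12 = 16.7%, 2/18 = 11.1%, 2/30 = 6.7% or 2/50 = 4.0%. A proportion over pooled levels says nothing about the dose at which the endpoint is judged.

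**The case against.** **The default rule is disclosed and may be harmless.** Columns are defined by a Day 1 dose these subjects never had, so any placement is a convention. Nothing in the documents shows a run-in-only subject above 800 mg, and the sponsor may drop the run-in visit once single-dose PK data suffice. The SAP was written with the clinical data in view, so its authors may have known whom the rule covers. All this is fair: the mislabelling is conditional, and Step 3 shows arithmetic rather than trial data. But the rule has no condition on dose, and assigning by the dose received avoids the problem at almost no cost.

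**No DLT table was promised.** Protocol 11.2.2 says only that the MTD will be described if reached. Cohort review sets it, and the planned tables do not alter it. Listings of DLTs, escalation-stage disposition and exposure exist and, with cohorts of at most six, might allow reconstruction. This stands as far as it goes: the gap is against the endpoint definition, not against a promised output. The documents do not say that those listings show dose, and counting by hand is a poor basis for reporting a primary endpoint.

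**Pooling is defensible when cohorts are tiny.** Many early levels may have N=1, where an incidence table adds little to a listing. True, and the reason to keep the 800 mg split as a summary. It does not excuse leaving the departure undeclared.

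**Tables by assigned dose misattribute later events.** Within-subject escalation is allowed, so an AE at a higher dose would be credited to the starting dose. This is correct. Assigned-dose tables restore the display by dose level; a table by dose at onset is a useful addition.

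**The DLT denominator is worded in two ways.** Protocol 3.8.1 retains under-dosed subjects if the cause was a DLT; Protocol 3.3 refers to drug-related toxicity. The difference is largely closed by Protocol 3.4, which makes failure to receive 75% of planned dose because of drug-related toxicity a DLT.

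**Conclusion.** The concern holds. The undeclared replacement of dose-level AE tables by a single 800 mg cut is plain on the text, and it places at least six levels in one column, provided that no step exceeded 100%. The default rule can produce a false column label; how many subjects it affects, and the direction of any bias, cannot be known from the documents. The DLT proportion behind the MTD cannot be read from any planned table, taking SAP Table 6 as the complete list. The MTD decision itself is unaffected, since it is taken at cohort review. The sponsor should correct this; it is a matter of reporting and transparency, not a flaw in the trial's design.

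**What to change.** - **SAP 9.2.1:** assign subjects without a Day 1 dose to the column of the run-in dose they actually received.
- **TEAE tables:** add the main ones (all, grade 3 or higher, treatment-related) by assigned dose level and schedule, as Protocol 11.2.2 requires. Keep ≤800/>800 mg as a summary.
- **DLT table:** add one table of DLT n/N by dose level and schedule, with the Protocol 3.8.1 definition as denominator.
- **SAP Section 13:** declare whatever departure from Protocol 11.2.2 remains.
- **Optional:** an AE table by dose at onset, because within-subject escalation is permitted.

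The cost is SAP wording and a few extra tables from data already collected. Some columns will be small, a number of them N=1, because escalation begins with single-subject cohorts. The added tables should therefore be labelled descriptive.
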